An Unscheduled Visit should also be performed for any participant who reports potential exposure to COVID-19. This visit should be performed within 48 to 120 hours of the suspected exposure to COVID-19.

Exposure to COVID-19 is defined as a participant who has had close contact (within 6 feet [2 meters] for a total of 15 minutes or more) to a person with laboratory-confirmed COVID-19 (or clinically compatible illness) or to a person who has tested positive for COVID-19 (laboratory confirmed) but has not had any symptoms.

Note: This is irrespective of whether the person with COVID-19 or the contact was wearing a mask or whether the contact was wearing respiratory PPE.

Arcturus Therapeutics, Inc.
Protocol ARCT-021-04, Version 6.0

ARCT-021
09 March 2022

[figure not shown]
An unscheduled clinic visit does not substitute for a participant's routine medical care. Therefore, participants should be encouraged to seek evaluation and care, if appropriate, from their usual provider.

Participants with confirmed COVID-19 should receive treatments/medications according to the standard of care.

The first Unscheduled Visit performed for the evaluation of COVID-19 symptoms or exposure starts the beginning of the COVID-19 surveillance period. Starting the day after the Unscheduled Visit, the participant will be contacted daily by telephone or by telemedicine visits until:

- An asymptomatic participant who has been exposed to COVID-19 has a negative RT-PCR test result
- A participant with symptoms of COVID-19 and a positive RT-PCR clinically recovers or 14 days have passed since onset of symptoms. For participants with ongoing illness 14 days later, the COVID-19 event will be followed to resolution and the frequency of calls and unscheduled visits will be based on clinical discretion.
- A symptomatic participant has two negative test (RT-PCR) results
- Should a participant who was exposed to COVID-19, whose RT-PCR test is negative go on to develop symptoms suggestive of COVID-19 within the next 14 days, the participant should have another Unscheduled Visit and receive repeat RT-PCR testing. If COVID-19 is confirmed, the participant will undergo the follow-up described above.

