6.4.1.1.7 Clinical Events of Special Interest

Clinical Events of Special Interest (CESI) are events relating to the detection of disease (SARS-CoV-2) activity relevant to the study vaccine. These events are analyzed separately from safety data; however, if the CESI demonstrates untoward signs or symptoms that, in the opinion of the Investigator, suggest the events are more likely related to study vaccine rather than to SARS-CoV-2, these signs/symptoms will be reported as AEs.

To be considered as a CESI of COVID-19 the following case definition adapted from the CBER Guidance: Development and Licensure of Vaccines to Prevent COVID-19 ([DHHS 2020](#)) must be met:

- The participant must have experienced at least 1 of the following systemic symptoms: fever ($\geq 38^{\circ}\text{C}$), chills, myalgia, headache, sore throat, congestion or runny nose, nausea or vomiting, diarrhea, fatigue, new olfactory and taste disorder(s), cough, shortness of breath, or difficulty breathing OR
- Clinical or radiographical evidence of pneumonia; AND
- The participant must have at least 1 test positive for SARS-CoV-2 by RT-PCR.

To be considered as a CESI of asymptomatic SARS-CoV-2 infection, a participant who demonstrates none of the COVID-19 symptoms described above but who tests positive for SARS-CoV-2 on PCR test or anti-nucleocapsid antibody test (if nucleocapsid antibody negative prior to entry into the study) will be counted.

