7.1 Estimands and Intercurrent Events

Possible intercurrent events are presented in [Table 7-1](#).

Table 7-1 Intercurrent Event Types

Label	Intercurrent Event (IcEv) Type
IcEv1 (Death)	Death due to any cause (including pneumonia) other than COVID-19.
IcEv2 (Missed dose)	Does not receive the second or booster vaccinations at Day 28 and Day 208, respectively.
IcEv3 (Immune-modifying)	Use of immune-modifying drugs or non-study vaccines which interfere with immunogenicity.
IcEv4 (Early infection)	Antigens or antibodies indicating exposure to SARS-CoV-2 prior to vaccination or early infection before Day 7. (This IcEv is particularly relevant to assessing immunogenicity.)
IcEv5 (Study infection)	Develops COVID-19 or asymptomatic SARS-CoV-2 infection on or after Day 7. (This IcEv is particularly relevant to immunogenicity and CESI events.)

Attributes for the primary safety and immunogenicity estimands with strategies for intercurrent events (IcEvs) are presented in [Table 7-2](#).

Table 7-2 Primary Safety and Immunogenicity Estimands With Rationale and Strategies to Address Intercurrent Events

Estimand Label	Estimand 1 (Safety)
Estimand Description	Count and percentage of vaccinated healthy adults who would develop MAAEs, NOCDs, SAEs, AEs leading to discontinuation/withdrawal, solicited AEs, and unsolicited AEs: These will be evaluated after each dose of study vaccine by priming vaccine study group (Group 1, 2, 3, and 4) and by booster vaccine received (ARCT-021, ARCT-154, ARCT-165, or placebo). A treatment policy strategy is used for assessing safety irrespective of an early infection within 7 days after the first vaccination or an infection during the study or missed subsequent vaccination. Infections and death are included in the endpoint (composite strategy).
Target Population	Participants receiving at least 1 dose of study vaccine (as defined by eligibility criteria).
Endpoint	Occurrence of MAAEs, NOCDs, AEs leading to discontinuation/withdrawal, SAEs, solicited, or unsolicited AEs: 
 Solicited AEs within 7 days of each vaccination (by Toxicity Grade, Appendix 13.4): Day 7, Day 35, Day 215 Unsolicited AEs within 28 days of each vaccination (by mild/moderate/severe severity): Day 28, Day 56, Day 236 MAAEs, NOCDs, SAEs, AEs leading to discontinuation/withdrawal from Vaccination 1 to Prior to Vaccination 2, Vaccination 2 to Prior to Booster Vaccination, Overall Prior to Booster Vaccination, and Post-booster Vaccination

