9.1. Adverse Events

Adverse Event (AE) collection will begin after the signing of informed consent; however, AEs that occur prior to the administration of first dose of study vaccine (i.e., non-treatment-emergent AEs) will be listed in the clinical study report. MedDRA version 23.0 or higher will be used for coding to System Organ Class (SOC) and Preferred Term.

Any case of confirmed COVID-19 or asymptomatic SARS-CoV-2 infection will be regarded as a Clinical Event of Special Interest (CESI) and entered on the CRF as an Adverse Event. Because CESI events are typically associated with the disease under study, they will not be reported as suspected unexpected serious adverse reaction (SUSAR) but on the CESI eCRF page.

Summaries of number of participants (%) with solicited AEs (by toxicity grade), safety laboratory assessments (by toxicity grade), unsolicited AEs (by severity and relatedness to study vaccine), MAAEs, NOCDs, and AEs leading to discontinuation/withdrawal will be presented and

also with a focus on those related to vaccine administration. All summaries will be evaluated by study treatment group as well as vaccine administration (first dose, second dose, booster dose).

Incomplete AE onset and end dates will be imputed according to the rules specified in [Appendix 2](#).

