13.5. Appendix 3: Estimands and Intercurrent Events

Possible intercurrent events are presented in the table below.

Table 13-3 **Intercurrent Event Types**

Label	Intercurrent Event Type
IcEv1 (Death)	Death due to any cause (including pneumonia) other than COVID-19.
IcEv2 (Missed dose)	Does not receive the second vaccination at Day 28 where second vaccination assigned was ARCT-021 or does not receive booster vaccination at Day 208 where booster vaccination assigned was active ARCT booster. It is not necessary to exclude placebo missed second doses as there is no impact.
IcEv3 (Immune-modifying)	Use of immune-modifying drugs or non-study vaccines which interfere with immunogenicity. Immune-modifying drugs will be determined from a medical review of medications taken during the study.
IcEv4 (Early infection)	
Priming vaccination period: Antigens or antibodies indicating exposure to SARS-CoV-2 prior to vaccination or early infection before Day 7. (This IcEv is particularly relevant to assessing immunogenicity.) Early infection is defined as follows:
 
 ○ Positive PCR saliva test at baseline OR ○ Positive PCR test at any time up to 7 days post-baseline OR ○ Positive SARS-CoV-2 baseline serostatus 
Booster vaccination period: Antigens or antibodies indicating exposure to SARS-CoV-2 prior to vaccination or early infection before Day 7 post booster vaccination. (This IcEv is particularly relevant to assessing immunogenicity.) Early infection for different boosters is defined as follows:
 
 ○ Positive PCR saliva test on Day 208 OR the booster vaccination OR ○ Positive PCR test at any time up to 7 days post-booster vaccination
IcEv5 (Study infection)	Develops COVID-19 or asymptomatic SARS-CoV-2 infection on or after Day 7. (This IcEv is particularly relevant to immunogenicity and CESI events.). Study infection is defined as COVID-19 infection recorded on the adverse event CRF page with start date on or after Day 7. The following AE preferred terms will be considered: Asymptomatic COVID-19, COVID-19, Suspected COVID-19. Positive MSD nucleocapsid antibody value of 5000 AU/mL or higher at any point after baseline (with start date on or after Day 7) will also be considered as on-study infection.

Attributes for the primary safety estimands with strategies for IcEvs are presented in Table 13-4 below.

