Estimand Label	Estimand 2 (Geometric Mean Titers/Concentrations)
Estimand Description	
The GMT of NAbs (primary) and BAbs (secondary) against SARS-CoV-2 up to Early Termination after first vaccination with ARCT-021 of each group (5.0, 7.5 µg, or placebo) and with/without booster dose in healthy adults.
 
Interest will lie in comparing the GMT of each dosing regimen to placebo based on the Geometric Mean Ratio (GMR).
 
The hypothetical strategy is used to estimate antibody levels had all scheduled vaccinations been received, and without subsequent SARS-CoV-2 infection or influence from immune-modifying drugs or non-study vaccines. The principal stratum strategy excludes those with active or early SARS-CoV-2 infection within 7 days after the first study vaccine administration.

Analysis Population	Vaccinated healthy adults (as defined by eligibility criteria) without active or early SARS-CoV-2 infection (infection within 7 days after the first vaccination).
Endpoint	Total NAbs (primary) and BAbs (secondary) specific for the SARS-CoV-2 measured pre- and post-priming vaccine administration (on Day 0, 14, 28, 42, 56, and 208) and following booster vaccine administration (Day 236, Early Termination).
Treatment Conditions	Placebo or 5.0 µg or 7.5 µg ARCT-021 administered on Day 0, Day 28; placebo, ARCT-021, ARCT-154, or ARCT-165 administered on Day 208.
Population-Level Summary	The GMT and GMR of comparisons of interest at each time point. GMR will compare responses in placebo-, ARCT-021-, ARCT-154-, and ARCT-165-vaccinated groups at relevant timepoints. For additional considerations on population-level summary see the SAP.
Intercurrent Event Strategy	
IcEv1 (Death)	Hypothetical strategy
IcEv2 (Missed dose)	Hypothetical strategy
IcEv3 (Immune-modifying)	Hypothetical strategy
IcEv4 (Early infection)	Principal stratum strategy (based on study phase)
IcEv5 (Study infection)	Hypothetical strategy
Rationale for Strategies	Hypothetical strategy is used to understand antibody levels achieved through receiving scheduled vaccination, without subsequent SARS-CoV-2 infection and without any influence from immune-modifying drugs or non-study vaccines. In estimation, the hypothetical uses a statistical model on the mITT (excluding data points following intercurrent events and not complete removal of all data for the participant).

Estimand Label	Estimand 3 (Rise/Seroconversion)

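### The SAP's on-study-infection rule (IcEv5) accepts the AE term Suspected COVID-19 without laboratory confirmation, so any unconfirmed case, including one that tested negative, would lose valid later antibody data

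*SAP*

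**What the plan says.** SAP Appendix 3, Table 13-3, defines the event this way: "Study infection is defined as COVID-19 infection recorded on the adverse event CRF page with start date on or after Day 7". It then names the qualifying records: "The following AE preferred terms will be considered: Asymptomatic COVID-19, COVID-19, Suspected COVID-19". A post-baseline N-antibody value of 5000 AU/mL or more "will also be considered as on-study infection". That is a second route into the category, not a confirmation of the first.

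The protocol words IcEv5 (Section 7.1, Table 7-1) as "Develops COVID-19 or asymptomatic SARS-CoV-2 infection on or after Day 7". Its definition of a COVID-19 clinical event of special interest (Section 6.4.1.1.7) requires a listed symptom or evidence of pneumonia, and in addition "The participant must have at least 1 test positive for SARS-CoV-2 by RT-PCR". SAP 9.1 likewise describes the cases entered as adverse events as confirmed COVID-19 or asymptomatic infection.

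For Estimands 2 and 3, SAP Table 13-5 assigns IcEv5 a hypothetical strategy. Estimation is on the mITT set, "excluding data points following intercurrent events and not complete removal of all data for the participant".

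**The concern.** Estimands 2 and 3 target the antibody response that would be seen with no later SARS-CoV-2 infection. Removing data after a real infection serves that target. Removing data from someone whom the trial's own tests show to be uninfected does not; it only discards valid neutralizing and binding antibody results.

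The rule as written allows this. It turns a site's unresolved suspicion into an infection and gives no way back when the tests are negative. It also departs from the protocol on an input to a primary endpoint without being declared as a change. The SAP Introduction says that the SAP prevails where the two differ, so the wider definition would be the one programmed.

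**Working it through.** No figure in the plan tests this point, so the check is mainly a comparison of texts, followed by an illustrative size.

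**1. Definitions side by side**

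| Place | What counts | Laboratory result needed? |
|---|---|---|
| Protocol Table 7-1, IcEv5 | COVID-19 or asymptomatic infection from Day 7 | Not stated there; no suspected category |
| Protocol 6.4.1.1.7, COVID-19 | Symptom or pneumonia, plus test | Yes, positive RT-PCR |
| Protocol 6.4.1.1.7, asymptomatic infection | No symptoms, plus test | Yes, positive PCR or N antibody |
| SAP Table 13-3, IcEv4 (priming) | Early infection | Yes, positive PCR or positive baseline serostatus |
| SAP Table 13-3, IcEv5 | AE term, including Suspected COVID-19, or N antibody at 5000 AU/mL or above | No, for the AE route |

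SAP Section 11 lists four changes from the protocol. None concerns IcEv5.

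**2. Can a test-negative episode reach the AE page?**
- Protocol 6.1 asks participants to report any listed symptom whatever its presumed cause. Confirmed symptoms lead to an Unscheduled Visit, except in the 7 days after the first vaccination.
- Seven of the nine solicited systemic AEs are on that symptom list: chills, diarrhea, fatigue, fever, headache, myalgia and nausea/vomiting. Arthralgia and dizziness are not.
- Protocol 6.4.1.1.4 makes an AE that leads to an Unscheduled Visit a medically attended AE, reported on the AE page.
- Protocol 6.1 foresees test-negative episodes: daily contact ends when "A symptomatic participant has two negative test (RT-PCR) results".

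Neither document says which term the site then records. The route to the AE page exists; the step to the preferred term Suspected COVID-19 is left open.

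**3. What one such record removes**

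If the event falls between the Day 28 and Day 42 visits, Days 42, 56 and 208 are lost: three of the five post-baseline priming-period samples (Days 14, 28, 42, 56, 208). The participant also enters the SAP 9.4 group identified as on-study infection.

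**4. Illustrative size**

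From the documents: planned arm size 2 × 75 = 150 over both age cohorts; SD 1.2 on the natural-log scale (SAP 4.2). Assumed, because the documents give neither: a fraction f = 2% to 5% of an arm wrongly flagged, with a GMT twice that of the rest of the arm.

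- Participants affected: 0.02 × 150 = 3; 0.05 × 150 = 7.5.
- Arm GMT after removal, relative to before: exp(−f × ln 2) = 0.986 for f = 0.02 and 0.966 for f = 0.05, a fall of about 1.4% to 3.4%.
- 95% interval of one arm's GMT: exp(1.96 × 1.2 / √150) = 1.21-fold either way.
- 95% interval of the GMR, exp(1.96 × 1.2 × √(2/n)), with a 5% loss in both arms: 1.312 to 1.321-fold at n = 150, and 1.468 to 1.483-fold at n = 75 (one age cohort).

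**The case against.** The strongest reply is that the governing sentence in Table 13-3 speaks of a recorded COVID-19 infection, and the term list only locates such records. SAP 9.1 describes these as confirmed cases. Chills or fatigue after a dose are solicited events; if they also qualify as medically attended, it is the solicited event that is captured again, and nothing recodes it as Suspected COVID-19. This stands to the extent that a reader might infer that symptomatic, RT-PCR-negative participants are in fact being classed as infected. The documents do not show that this happens, or how often; the number may be zero. They show only that the rule would not prevent it.

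A reader might also infer that the two-dose arms would be hit hardest and that the choice of dose would be biased. Neither is supported. Protocol 1.5 reports that solicited AEs decline slightly after the second dose, and no link between reactogenicity and titre is given. The 5 µg single dose for Phase 3 was selected as of protocol version 4.0, whereas this SAP governs the final analysis and postdates a June 2022 data review.

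Finally, including suspected cases is a cautious choice: a missed infection contaminates titres, especially under placebo. Protocol 6.1 says that the central saliva RT-PCR is not a diagnostic test, and visits may be by telemedicine. This justifies keeping suspected cases that have no test result. It does not justify keeping those with negative RT-PCRs and N antibody below the cut-off throughout.

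**Conclusion.** The point holds as a defect of definition. IcEv5 in the SAP is wider than the protocol's IcEv5 and its RT-PCR case definition, is out of line with the laboratory-based IcEv4 in the same table, and is not declared in Section 11. Where it applies to a test-negative participant, it removes valid data from the primary and secondary antibody summaries.

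The effect on results is probably small. Under the assumed 2% to 5% rate and two-fold titre excess, the shift in GMT is well inside the sampling error, and the interval for the GMR barely widens. Both assumptions are illustrative. In SAP 9.4 the effect is on the denominator only: the numerator still depends on a yes to the question about symptoms of confirmed COVID-19, so a test-negative participant is not thereby counted as a confirmed symptomatic case. The reason to act is agreement between the rule, the estimand and the protocol, at little cost.

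**What to change.** In SAP Table 13-3:

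- Keep the terms COVID-19 and Asymptomatic COVID-19 as triggers, together with the N-antibody criterion, and add a positive RT-PCR on or after Day 7. Demanding laboratory proof for every term could lose genuine diagnoses made outside the study, which Protocol 2.3 collects.
- Count Suspected COVID-19 only when it is supported by a positive RT-PCR or N antibody of at least 5000 AU/mL, or when the episode has no RT-PCR result.
- Do not count it when the RT-PCRs for the episode were negative and N antibody stayed below the cut-off.

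Use the same flag for the on-study-infection group in SAP 9.4, and list the definition in Section 11.

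The cost is a short change to the table, an entry in Section 11, and a merge with RT-PCR and N-antibody results that the schedule of events already collects. The downside is small: a true infection with a false-negative RT-PCR and no N seroconversion would stay in the analysis.

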6.1. Demographics

Descriptive statistics will be calculated for the following continuous demographic and baseline characteristics: age (years), weight (kg), height (cm), body mass index (BMI) (kg/m²). The number and percentage of participants will be provided for categorical variables such as age group, sex, race, ethnicity, country, site, baseline SARS-CoV-2 serostatus (positive/negative/missing) defined by nucleocapsid testing at Day 0, and evidence of viral shedding as measured by a saliva RT-PCR test at Baseline.

Baseline SARS-CoV-2 serostatus is defined as SARS CoV-2 nucleocapsid (N) antibody level of greater or equal to 5000 (AU/mL). This threshold is defined by BioA laboratories based on levels for a clinical definition of PCR-confirmed COVID-19 infection.

The number and percentage of participants will be summarized by site and by stratification factor at randomization (i.e., ≥ 18 to <56 years; ≥ 56 years) separately based on the Safety set for the priming vaccination period, re-enroll subjects, and booster vaccination period.

Summaries will be provided separately based on the Safety set, mITT set, PP set, mITT-CMI subset by study treatment group. The summaries will be repeated by study treatment group for re-enrolled subjects based on Safety set and for the booster vaccination period based on the Booster Safety set, Booster mITT set, Booster PP set, Booster mITT-CMI subset. Summary of demographics by ≥ 18 to <65 years vs. ≥ 65 years will also be provided for the priming vaccination period.

For screened failure participants, age (years), gender, race and ethnicity will be presented in a listing.

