9.4. COVID-19 exposure and symptoms

The number and percentage of participants reporting symptoms of potential COVID-19 (Yes/No/missing) from CRF page SARS-CoV-2 or COVID-19 Symptoms Assessment will be summarized by treatment groups for the Safety analysis set. For participants reporting ‘Yes’, all symptoms will also be summarized by frequency.

For participants identified as on-study infection, the number and percentage of participants reporting ‘Yes’ to the question Any Symptom of Confirmed COVID-19 from CRF page Clinical Event of Special Interest will be reported by treatment groups and by each priming vaccination period. All symptoms will also be summarized by frequency.

Incidence of COVID-19 and incidence of asymptomatic infection based on the Adverse Event CRF page will be summarized for the following time periods: after first study vaccine dose to 14 days after first study vaccine dose, between 14 days after first study vaccine dose to 2nd study vaccine dose, and after 2nd study vaccine dose to booster vaccine / early termination prior to Day 208 visit. This will also be summarized for re-enrolled subjects separately.

Incidence of COVID-19 and incidence of asymptomatic infection after booster vaccine to early termination after booster vaccine based on the Adverse Event CRF page will be summarized. For subjects not receiving a booster vaccination, events from Day 208 through early termination will be summarized under the Booster Placebo/No Booster group.

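### The SAP's antibody rule for on-study infection omits the protocol's baseline-negative condition, so participants seropositive at entry can be placed in the SAP 9.4 symptom table for on-study infections

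*SAP*

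**What the plan says.** SAP Appendix 3, Table 13-3, defines two infection events that matter here.

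- **IcEv5 (study infection)** opens with the intent: "Develops COVID-19 or asymptomatic SARS-CoV-2 infection on or after Day 7". It is then identified in two ways. One is Adverse Event page entries: "The following AE preferred terms will be considered: Asymptomatic COVID-19, COVID-19, Suspected COVID-19". The other is serological: a "Positive MSD nucleocapsid antibody value of 5000 AU/mL or higher at any point after baseline", qualified by a start date no earlier than Day 7. No baseline condition is attached to the serological part.
- **IcEv4 (early infection)**, priming period, includes "Positive SARS-CoV-2 baseline serostatus". SAP 6.1 fixes the cut-off: "Baseline SARS-CoV-2 serostatus is defined as SARS CoV-2 nucleocapsid (N) antibody level of greater or equal to 5000 (AU/mL"). This is the IcEv5 threshold.

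Protocol 6.4.1.1.7 counts asymptomatic infection detected by N antibody only "if nucleocapsid antibody negative prior to entry into the study". SAP Section 11 lists four changes from the protocol, and this is not one of them. SAP Section 1 says the SAP governs where the two differ.

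SAP 9.4 uses the flag to define a reported group: "For participants identified as on-study infection, the number and percentage of participants reporting" a symptom on the Clinical Event of Special Interest (CESI) page, by treatment group and priming period.

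**The concern.** N antibody at or above 5000 AU/mL after baseline shows that infection occurred at some time. It shows infection during the study only if the participant was below the cut-off at entry. The protocol has that safeguard and the SAP rule does not.

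Such participants can be in the trial. Protocol 4.1.2 excludes known prior infection, but testing for past exposure at screening is at the investigator's discretion, and SAP 6.1 plans to tabulate baseline serostatus as positive, negative or missing.

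At stake is one descriptive output, the 9.4 symptom summary among on-study infections. A person whose infection predates vaccination has no reason to have a CESI symptom entry. Including that person enlarges the group without adding to the symptomatic count.

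**Working it through.** The plan states no figure to reproduce; the check is one of definitions. Take a participant with N at or above 5000 AU/mL on Day 0 and again on Day 14, with no new infection.

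1. **IcEv4, priming period:** met, through baseline serostatus (SAP 6.1 and Table 13-3).
2. **IcEv5, serological part:** depends on what start date means for a laboratory value, which the SAP does not define.
   - If it means the sample date, the condition is met. It removes almost nothing, because the first scheduled post-baseline antibody draw is Day 14 (SAP Appendix 1).
   - If it means onset of positivity, this participant does not qualify.
3. **Precedence between IcEv4 and IcEv5:** none stated.

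Tracing the participant through the outputs:

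| Output | Effect of the IcEv5 flag |
|---|---|
| Priming antibody estimands 2 and 3 | None: removed through IcEv4 (principal stratum) |
| CMI summaries (SAP 8.3.2) | None: prior infection at first vaccination is excluded outright |
| COVID-19 and asymptomatic infection incidence (SAP 9.4) | None: taken from the Adverse Event page |
| CESI symptom table (SAP 9.4) | Can enter as an on-study infection |
| Booster-period antibody summaries | The booster IcEv4 bullets rely on PCR only, so IcEv5 may be what removes this participant |

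A participant with missing baseline N is not caught by the serostatus part of IcEv4 and can be flagged by IcEv5 alone.

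**Denominator in the symptom table.** SAP 9.4 does not state it. If it is the flagged participants, old infections lower the symptomatic percentage. If the SAP Section 4 default applies (the treatment group within the analysis set), they leave the percentage unchanged.

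**Illustration only.** Let p be the proportion seropositive at baseline, i the on-study infection rate in the rest, and k the share of baseline positives still at or above the cut-off. With 579 enrolled (Protocol 1.5):

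- old infections flagged = k × 579p
- new infections = (579 − 579p) × i
- old share = old / (old + new)

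None of p, i or k is in the documents. Assumed ranges are p 1% to 10%, i 2% to 10%, k 0.5 to 1.0.

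- Lowest share (p = 1%, i = 10%, k = 0.5): old 0.5 × 5.8 = 2.9; new 573.2 × 0.10 = 57.3; share 2.9 / 60.2 = 5%.
- Intermediate (p = 3%, i = 5%, k = 1): old 17.4; new 561.6 × 0.05 = 28.1; share 17.4 / 45.5 = 38%.
- Highest share (p = 10%, i = 2%, k = 1): old 57.9; new 521.1 × 0.02 = 10.4; share 57.9 / 68.3 = 85%.

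With flagged participants as denominator and no CESI symptom entry for old infections, the printed symptomatic share is the true share times (1 − old share): a multiplier of 0.95, 0.62 and 0.15 in these three cases.

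**The case against.** The strongest reply is that the plan already deals with prior infection. The IcEv5 lead sentence speaks of developing infection on or after Day 7, and its serological part carries a start-date qualifier. If that qualifier means onset of positivity, baseline positives are out. IcEv4 removes them from the priming antibody summaries, and the CMI text excludes them explicitly. The symptom table counts CESI entries, and CESI cases follow the protocol definition, which has the baseline-negative condition. The study tests no hypotheses.

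Most of this stands and limits the point to one table. It does not close the gap. The qualifier is undefined for a laboratory value and does nothing on the sample-date reading; no precedence is stated; and IcEv4 is not applied to the 9.4 symptom table.

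The reply is also right that a baseline-negative condition alone could do harm. In the booster period it could readmit baseline-seropositive participants whom only IcEv5 now removes.

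A reader might infer further that IcEv5 should reject unconfirmed Suspected COVID-19 entries and read RT-PCR results directly. The documents do not make either a defect. SAP 9.1 has confirmed and asymptomatic infections entered as adverse events, so PCR-positive cases should reach IcEv5 through those terms. Setting aside later data after a suspected infection is a defensible choice for an estimand framed as no subsequent infection.

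**Conclusion.** The point holds in limited form. The serological part of IcEv5 departs from Protocol 6.4.1.1.7 without being listed as a change. On the sample-date reading, baseline-seropositive participants can be reported among on-study infections in the 9.4 symptom table. If flagged participants are the denominator, the symptomatic share is biased downward.

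The size cannot be found from the documents. The 5% to 85% range rests wholly on assumed rates and shows only that the effect could be trivial or large.

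A reader might infer that infection counts by arm are distorted, or that a vaccine-placebo difference in infection is diluted. The documents do not support this: both incidence summaries in SAP 9.4, priming and booster, are taken from the Adverse Event page, and no incidence comparison listed there uses the N-antibody flag. Nor are the priming antibody results affected for participants with a known positive baseline.

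**What to change.** In SAP Table 13-3 and SAP 9.4:

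- Define the serological part of IcEv5 as the first N value at or above 5000 AU/mL, in a sample taken on or after Day 7, in a participant with baseline N below 5000 AU/mL. This also replaces the undefined start date.
- State how a missing baseline N is handled.
- State that IcEv4 takes precedence over IcEv5, and that participants seropositive at baseline stay excluded as IcEv4 from the booster-period antibody summaries.
- Use this flag for the 9.4 symptom table, and name that table's denominator.
- Record the definition in SAP Section 11 if any departure from Protocol 6.4.1.1.7 remains.

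The cost is SAP wording and a small change to the flag derivation. Day 0 and later N results are already collected, so no new data are needed.
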